2.7.3 Handling of missing values/censoring/discontinuations

Missing body weight at Week 24 will be imputed using the multiple imputation method as described in Section 2.5.3.

Repeated measure ANCOVA models, which use all available data, will be used to analyze other secondary variables. The approach yields valid results, i.e. confidence intervals with correct coverage and tests with the correct size under a missing at random (MAR) process (Siddiqui et.al. 2009).

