### **5.5.6 Rescue medication**

During Epoch 3 and Epoch 4, rescue medication may be used in addition to ongoing study medication for those subjects with T2DM whose glycemic control is deteriorating. The subject must come in for an unscheduled visit to have a sample drawn for FPG & HbA1c measurement performed by the central laboratory if:

- Self-measured FPG on two consecutive occasions exceeds the limits in [Table 5-1](#).
- The result from a blood sample analyzed by the central laboratory exceeds the limits described in [Table 5-1](#).

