**Table 5-1      Rescue criteria for FPG or HbA1c (subjects with T2DM)**

Timeframe	Parameter	Value	Action
Between V201 (Randomization) and V204 (Week 8)	FPG	> 240 mg/dL (13.3 mM)	Unscheduled visit for central laboratory parameter measurement.
Between V204 (Week 8) and V205 (Week 12)	FPG	> 220 mg/dL (12.2 mM)	If elevation confirmed by central laboratory: background OAD to escalate to the maximum approved dose, followed by addition of another allowed OAD (eg a DPP-4 inhibitor used according to the label or insulin as per the investigator's discretion)
Between V205 (Week 12) and V399 (Week 48)	FPG	> 200 mg/dL (11.1 mM)	
Between V205 (Week 12) and V399 (Week 48)	HbA1c	> 8 %	

If the results confirm the exceeded limits, first the background OAD should be escalated to the maximal approved dose in steps if clinically indicated, followed by addition of rescue medication.

Rescue medication, a dipeptidyl peptidase-4 (DPP-4) inhibitor or insulin, should be used according to the local label. Rescue medication must be provided locally.

Rescued subjects will continue to participate in the study to allow for assessment of exposure and safety of LIK066.

Use of rescue medication must be recorded on the Rescue Medication eCRF.

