### **End of study analysis**

The duration of overall treatment period (Epoch 3 + Epoch 4) as well as the duration of Epoch 4 will be summarized by treatment group both descriptively and by duration-category for subjects in the SAF who enter the study Week 24 to Week 48 period (Epoch 4), respectively.

Concomitant medications and rescue medications subjects take during Epoch 4 will be similarly summarized for subjects in SAF who enter Epoch 4.

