2.4.2 Prior, concomitant and post therapies

Week 24 analysis

Prior medications are defined as any drugs taken and stopped prior to the first dose of study medication. Concomitant medications for Epoch 3 are any medications given at least once between the day of first dose of double-blind study medication and the end of Epoch 3, including those which started pre-BL and continued into the treatment period.

The number and percentage of subjects receiving prior and concomitant medications will be summarized by treatment group and overall in the SAF in separate tables by therapeutic class and preferred term.

The number and percentage of subjects taking rescue medication, and duration of exposure to rescue medication during Epoch 3 will be summarized by treatment group.

The number and percentage of subjects on anti-diabetic medications at BL (randomization visit) will be summarized by treatment, glycemic status, and medication types:

- Any anti-diabetic medication (insulin or OADs)
- Insulin
- OADs (used as single pills)
 - Metformin
 - SU - Sulfonylureas (including Sulfonamides)
 - AGIs
 - TZDs
 - DPP-4 inhibitors
- Combination of OADs
 - Phenformin + SU
 - Metformin + SU
 - Metformin + TZD
 - SU + TZD
 - Metformin + DPP-4i
 - Metformin + AGI
 - DPP-4i + TZD
- Other

The search criteria for the anti-diabetic medications by type are included in the appendix.

The use of prohibited medications, defined in Table 2-2 below, will also be summarized.

Table 2-2 Prohibited medication for reporting

Prohibited Medication	Drug record No. or ATC
Clarithromycin	00984601
Telithromycin	01548701
Itraconazole	00780701
Ketoconazole	00532501
Voriconazole	01510101
Posaconazole	01762801
Probenecid	00045101
Valproic Acid	00228501
Mefenamic Acid	00044201
SGLT2 inhibitors	A10BK

Prohibited Medication	Drug record No. or ATC
GLP-1 receptor agonists	A10BJ
Weight loss medication	A08A

End of study analysis

Concomitant medications for Epoch 4 are any medications given at least once between the start and the end of Epoch 4, including those which started before and continued into Epoch 4. Concomitant medications subjects take during Epoch 4 will be similarly summarized for subjects in SAF who enter Epoch 4.

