2.5.4 Supportive analyses

As a sensitivity analysis, the dose-response modeling as described in Section 2.5.2 will be conducted in the PPS as well. In addition, the same dose-response modeling will be conducted in the FAS using on-treatment weight data only. On-treatment data refer to those collected during the double-blind period, and prior to or within 7 days of the final study medication intake date in Epoch 3.

Summary statistics for body weight will be presented by visit and treatment for observed and imputed values. The summary statistics n, mean, standard deviation, median, minimum, maximum, Q1 and Q3 will be presented for the BL values and similarly for absolute values at post-BL and percent changes from BL to the post-BL visits. Summary statistics for body weight will also be presented by visit and treatment for observed values by subgroups of interest: age group, gender, BMI categories and region.

Figures will be produced to visually show the raw and the imputed mean percent changes as well as the estimated mean percent changes from the dose response modeling by visit over 24 weeks of Epoch 3 for each treatment group.

In addition, the individual patients' percent change in body weight from BL at Week 24 will be depicted by waterfall plot as appropriate.

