For changes from BL at Week 24 in HbA1c, FPG, SBP, DBP, waist circumference and 24-h UGE, a repeated measure ANCOVA model with treatment, visit, stratification factor (normoglycemic, dysglycemic, and T2DM), pooled center or region, and treatment by visit interaction as fixed-effect factors, BL and BL by visit interaction as covariates, and a common unstructured covariance matrix among visits between treatments will be performed separately for each variable. The adjusted mean changes at Week 24 within each treatment, the differences in mean changes at Week 24 between the LIK066 and placebo treatments, and their 95 % confidence intervals obtained from the above model will be presented. The analysis is based on likelihood method with an assumption of MAR for missing data.

The same repeated measure ANCOVA model will be fitted for each stratum (normoglycemic, dysglycemic, and T2DM) as well, and the adjusted mean changes at Week 24 within each treatment, the differences in mean changes at Week 24 between the LIK066 and placebo treatments for each stratum, and their 95% confidence intervals obtained from the above models will be presented by strata for each efficacy endpoint.

Similar repeated measure ANCOVA models will be performed for percent changes of lipid parameters and \log_{10} transformed hsCRP from BL at Week 24.

Summaries of absolute values and change from BL by treatment group and visit will be presented for all secondary efficacy variables for all subjects and by strata. Figures will be produced to visually show the raw mean changes by visit over 24 weeks of Epoch 3 for each treatment group, for overall and by strata separately.

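### HbA1c and FPG models include values after treatment intensification that these endpoints trigger, and no supplementary Week 24 estimate shows the effect on the T2DM comparison

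*SAP*

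**What the plan says.** Protocol 5.5.6 provides that in Epochs 3 and 4 "rescue medication may be used in addition to ongoing study medication for those subjects with T2DM whose glycemic control is deteriorating". Table 5-1 sets the triggers: FPG above 240, 220 or 200 mg/dL depending on the period, and HbA1c above 8 % from Week 12 to Week 48. After central-laboratory confirmation the order is fixed. Background oral therapy is escalated first, and a DPP-4 inhibitor or insulin follows. Protocol 3.1.1 also allows existing insulin to be up-titrated.

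On follow-up, Protocol 5.5.6 says: "Rescued subjects will continue to participate in the study to allow for assessment of exposure and safety of LIK066". It adds: "Use of rescue medication must be recorded on the Rescue Medication eCRF".

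SAP 2.7.2 places all secondary analyses in the FAS. SAP 2.7.2.1 gives one repeated-measures model for HbA1c and FPG at Week 24, and then: "The same repeated measure ANCOVA model will be fitted for each stratum (normoglycemic, dysglycemic, and T2DM) as well". On data use, SAP 2.7.3 says: "Repeated measure ANCOVA models, which use all available data, will be used to analyze other secondary variables".

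The restricted-data analyses in SAP 2.5.4 concern body weight. One uses the PPS. In the other, "the same dose-response modeling will be conducted in the FAS using on-treatment weight data only", with the cut tied to the last study-drug intake rather than to rescue.

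On rescue reporting, SAP 2.4.2 keeps the Epoch 3 table: "The number and percentage of subjects taking rescue medication, and duration of exposure to rescue medication during Epoch 3 will be summarized by treatment group". For Epoch 4, Protocol 9.3 planned: "Concomitant medications and rescue medications subjects take during Epoch 4 will be similarly summarized". SAP 2.4.2 now has only concomitant medications for Epoch 4.

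**The concern.** The event that alters later HbA1c and FPG values is itself triggered by high HbA1c or FPG. If the drug lowers glucose, more subjects on placebo and on weak doses should cross a limit and be intensified. Their later values then reflect added glucose-lowering treatment, and the placebo mean moves towards the drug mean.

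Protocol 2.2 makes the comparison of HbA1c and FPG with placebo, overall and by glycemic subgroup, a secondary objective. SAP 1.1 says that the Week 24 report will support end-of-phase-2 discussions. A reader who sees a small glycemic difference in the T2DM stratum cannot tell how much of it is due to a weak drug effect and how much to intensification on placebo. The retained Epoch 3 rescue table shows who received a rescue drug. It does not show how far the estimate moved, and it does not cover subjects who only had oral therapy escalated.

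**Working it through.** The plan states no figure on this point, so there is none to reproduce. The calculation below gives scale only.

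**From the documents.** Placebo and each double-allocation arm have about 72 subjects, and each single-allocation arm about 36 (Protocol 5.2). Each of three strata should hold at least 30 % (Protocol 5.3), so the T2DM share is 30-40 %. T2DM subjects then number 72 × 0.30 = 22 to 72 × 0.40 = 29 on placebo, and 36 × 0.30 = 11 to 36 × 0.40 = 14 in a single-allocation arm.

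**Assumed, not in the documents.**
- Baseline HbA1c is normal with mean 7.2 or 7.6 and SD 0.8 or 1.0, limited to 6.0-10.0.
- Week 12 is baseline plus 0 or -0.3, plus noise with SD 0.6 or 0.8, minus 0.6 on drug.
- Intensification lowers HbA1c by 0.4-0.8 point.
- Between 25 % and 100 % of those above 8 % are intensified.

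**Step 1: who crosses 8 %.** Over the 16 scenarios, 15-39 % on placebo and 5-22 % on drug are above 8 % at Week 12. The difference is 0.098 to 0.191.

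**Step 2: dilution in the T2DM stratum** = difference × share intensified × gain.
- 25 % intensified: 0.098 × 0.25 × 0.4 = 0.010 to 0.191 × 0.25 × 0.8 = 0.038.
- 50-100 % intensified: 0.098 × 0.5 × 0.4 = 0.020 to 0.191 × 1.0 × 0.8 = 0.153.

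The range is about 0.01-0.15 point on an assumed effect of 0.6. In the overall population it is multiplied by the T2DM share: 0.010 × 0.30 = 0.003 to 0.153 × 0.40 = 0.061. If intensification rates are equal, it is zero.

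**Step 3: precision of one dose comparison** = 1.96 × SD × √(1/n1 + 1/n2).
- Assumed SD 0.8, 29 vs 29: 0.41.
- Assumed SD 1.2, 11 vs 22: 0.87.

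**Step 4: FPG**, with an assumed gain of 10-25 mg/dL and 50-100 % intensified: 0.098 × 0.5 × 10 = 0.5 to 0.191 × 1.0 × 25 = 4.8 mg/dL. The half-width is 18 (assumed SD 35, 29 vs 29) to 33 mg/dL (assumed SD 45, 11 vs 22).

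**Step 5: where to censor.** Two-visit simulations (Weeks 12 and 24) used a true difference of -0.60.
- If everyone intensified receives a dated rescue drug, all-data estimates are -0.45 to -0.59, and censoring at rescue start gives -0.59 to -0.61.
- In a further run, all subjects above 8 % are intensified, but 75 % have oral escalation only, with the same gain, and 25 % have a rescue drug. All-data estimates are then -0.469 to -0.554, and censoring at rescue start gives -0.481 to -0.560. It moves the estimate by only 0.006-0.013.
- At a 50/50 split it moves the estimate by 0.016-0.031.
- Censoring at the exceedance itself returns about -0.59 to -0.60.

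The good recovery is partly built in, because in these simulations intensification depends only on the observed Week 12 value. The simulations show which censoring point captures the intensification. They do not show that any such estimate would be unbiased in this trial.

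**The case against.** The strongest reply is that the all-data model is a choice, not an error. It estimates the effect of assignment with whatever background treatment follows, and that question is legitimate. SAP 2.6 names no key secondary objective. The expected shift is smaller than the uncertainty of any single dose comparison, and every input behind it is assumed. Protocol 5.5.6 requires confirmation and stepwise escalation before a rescue drug, so the upper end of the range is unlikely. Early FPG rescue is also limited by the randomization criterion for sulfonylurea and insulin users (Protocol 4.2, exclusion 26). The efficacy sections never mention rescue, so the inclusion of later values is inferred from the use of all available FAS data, continued follow-up and the absence of a censoring rule.

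All of this stands. It limits the point to a cheap supplement. It does not remove it, because nothing planned shows how far the estimate moves.

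Four stronger readings are tempting and not supported:
- A reader might infer that the planned model is invalid. It is a valid treatment-policy estimate.
- A reader might infer that the primary result is compromised. The primary test and target dose selection rest on weight (Protocol 9.4.2) and are not directly affected.
- A reader might infer that censoring at the rescue-drug start would recover the drug effect. The required order of escalation contradicts this.
- A reader might infer that the Epoch 4 rescue summary was dropped without disclosure. The SAP document history records the removal under May 11, 2018, and rescue drugs taken in Epoch 4 should still appear, unflagged, in the concomitant-medication table. Only the entry in SAP section 4, which lists the hsCRP change alone, is missing.

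**Conclusion.** The point holds as a modest, inexpensive improvement for secondary endpoints. The HbA1c and FPG models include values after intensification that those endpoints trigger, and no supplementary estimate is planned. The likely effect is a dilution of about 0.01-0.15 HbA1c point in the T2DM stratum, against a half-width of 0.41-0.87 for one dose. For FPG it is about 0.5-4.8 mg/dL against 18-33 mg/dL.

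These sizes rest on assumed HbA1c and FPG distributions, an assumed drug effect, an assumed share intensified and an assumed gain. The direction rests on intensification being commoner on placebo than on drug. The trigger makes that likely, but the documents do not show it.

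**What to change.** **Main change, SAP 2.7.2.1.** Keep the planned model. Add one supplementary Week 24 analysis each for HbA1c and FPG, in the T2DM stratum and overall, with the same repeated-measures model. Set to missing all values after the first central-laboratory-confirmed Table 5-1 exceedance that leads to oral-drug escalation, insulin up-titration or a rescue drug. If intensification dates are not available, set to missing all values after the confirmed exceedance. This fallback may be needed, because Protocol 6.3 specifies dates only for medications started after study start, and dose changes to existing drugs may not be dated. Dose adjustments made for safety under Protocol 3.1.2 and 3.1.3 should not count as a censoring event. Label the analysis post hoc, because the document history shows that Week 24 results existed before this SAP version was released.

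**Housekeeping.** List the removal of the Epoch 4 rescue summary in SAP section 4, or restore the table.

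**Cost.** One extra model per endpoint and population, and one line or one table. The standard error rises. In simulation it was 3-25 % larger for censoring at rescue start, and it would be larger still when all exceedances are censored. The estimate relies on missing at random given earlier values. That is less secure where the confirming sample comes from an unscheduled visit outside the by-visit model, or where FPG triggers the censoring of HbA1c.

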2.8 Safety analyses

All Week 24 safety analyses will be performed in the SAF, and all End of study safety analyses will be performed for subjects in the SAF who enter Epoch 4.

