## 2.2 Secondary objective(s)

1. To assess the responder rates according to percent decrease in body weight either  $\geq 5\%$  or  $\geq 10\%$ , from BL at Week 24, for the overall population and each of the subgroups (normoglycemic subjects, dysglycemic subjects and subjects with T2DM, see [Section 9.5.1](#)).
2. To assess the dose-response relationship for weight loss in normoglycemic subjects, dysglycemic subjects and subjects with T2DM after 24 weeks of treatment (see [Section 9.5.1](#)).
3. To evaluate the effect of all LIK066 doses and regimens *vs* placebo (see [Section 9.5.1](#)) for the overall population and by subgroups (normoglycemic subjects, dysglycemic subjects and subjects with T2DM, see [Section 3.1](#)) after 24 weeks of treatment and between Week 24 and Week 48 on:
  - Waist circumference, see [Section 6.4.2](#).
  - Change from BL in glycated hemoglobin A1c (HbA1c), see [Section 6.4.3](#).
  - Change from BL in fasting plasma glucose (FPG), see [Section 6.4.4](#).
  - Changes in systolic blood pressure (SBP) and diastolic blood pressure (DBP), see [Section 6.4.5](#).
  - Changes in the fasting lipid profile and high sensitivity C-reactive protein (hsCRP, see [Section 6.4.6](#)).
  - 24-h urinary glucose excretion (UGE) in a subset of subjects (see [Section 6.4.7](#)).
4. To evaluate the change in weight and other efficacy parameters listed in #3 in the overall population and by subgroups by LIK066 treatment *vs* placebo (see [Section 9.5.1.2](#)) between Week 24 and Week 48 (in Epoch 4, see [Section 3.1.3](#)).
5. To evaluate safety (adverse events (AEs) and laboratory parameters) and tolerability of LIK066 over 24 weeks of treatment and over 48 weeks of treatment for all subjects (see [Section 9.5.2](#)).
6. To evaluate AEs of interest and laboratory data (see [Section 9.5.2.2](#)) in subjects treated with LIK066 25 mg qd, 35 mg qd or placebo between Week 24 and Week 48 (during Epoch 4).
7. To evaluate 24-h urinary calcium and phosphorus excretion after 24 weeks of treatment and after 48 weeks of treatment in a subset of subjects.
8. To evaluate the pharmacokinetics (PK) of LIK066 (see [Section 6.6.3](#) and [Section 9.5.4](#)).

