#### **9.5.2.2 End of study analysis**

All safety analyses will be performed for subjects in the SAF who enter Epoch 4.

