### **AEs**

The number and percentage of subjects having AEs, SAEs, AEs leading to study medication permanent discontinuation and other significant AEs occurred during Epoch 4 will be summarized and presented by treatment. Similar summaries will be provided for events occurred during the overall 48 weeks of Epoch 3 plus Epoch 4.

The AEs of interest, including those related to potential/identified risks as specified in the DSPP, will be summarized as appropriate separately.

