2.2 Analysis sets

Screened set (SCR): the SCR consists of all subjects who signed the ICF.

Randomized set (RAN): All subjects who have received a randomization number, regardless of receiving trial medication.

Run-in set (RUN): All subjects who enter the run-in epoch.

Full analysis set (FAS): the FAS comprises all subjects to whom study treatment has been assigned, except those who are not qualified for randomization but were inadvertently randomized into the study and did not take any study drug. Following the intent-to-treat principle, subjects will be analyzed according to the treatment assigned to at randomization.

Safety set (SAF): the SAF includes all subjects who received at least one dose of study medication. Subjects will be analyzed according to treatment received. Note that the safety set allows the inclusion of non-randomized subjects who received the study drug in error.

Per-protocol set (PPS): the PPS is a subset of the FAS. It consists of all randomized subjects in the FAS who have been exposed to study medication for at least 22 weeks and have no major protocol deviations (PDs) affecting the primary endpoint analysis.

Randomized set – Epoch 4 (RAN-Epoch 4): all randomized subjects who have been assigned a treatment in Epoch 4.

Full analysis set – Epoch 4 (FAS-Epoch 4): all RAN-Epoch 4 subjects, excluding those who did not take any Epoch 4 study medication.

Safety set – Epoch 4 (SAF-Epoch 4): all SAF subjects who received at least one dose of Epoch 4 study medication.

Protocol deviations will be pre-specified prior to un-blinding treatment codes for analyses. See Appendix Table 5-2 and Table 5-3 for list of protocol deviations and criteria that lead to exclusion from analysis sets, and related rules of exclusion criteria of analysis sets.

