Week 24 on-treatment AEs are defined as any treatment-emergent AEs occurred while patients were on Epoch 3 treatment (captured using treatment start and end date). On-treatment AEs, serious AEs, fatal AEs, AEs leading to study drug discontinuation, and AEs of special interest will also be summarized.

End of study analysis

A treatment-emergent AE for the End of study analysis is defined as any AE that develops after the start of Epoch 4 or any event already present in Epoch 3 that worsens following exposure to the study treatment during Epoch 4. AEs occurring after treatment discontinuation will also be considered as treatment-emergent AEs. The number and percentage of subjects having AEs, SAEs, AEs leading to study medication permanent discontinuation and study drug interruption occurring after start of Epoch 4 will be summarized and presented, in similar way as for the Week 24 analysis.

Overall treatment emergent AEs for the overall 48 weeks of Epoch 3 plus Epoch 4 by 10 randomized treatments will be generated.

All AEs in the database will be listed by 10 randomized arms. The listings will include those AEs reported during the run-in epoch, and AEs reported after study completion or discontinuation.

Legal requirement for AE reporting

For the legal requirements of ClinicalTrials.gov and EudraCT, two required tables on treatment emergent AEs which are not SAEs with an incidence greater than 2% and on treatment emergent SAEs and SAEs suspected to be related to study treatment will be provided by system organ class, preferred term, and 10 randomized treatment arms on the SAF for overall study duration.

If for a same patient, several consecutive AEs (irrespective of study treatment causality, seriousness and severity) occurred with the same SOC and PT:

- a single occurrence will be counted if there is ≤ 1 day gap between the end date of the preceding AE and the start date of the consecutive AE
- more than one occurrence will be counted if there is > 1 day gap between the end date of the preceding AE and the start date of the consecutive AE

For occurrence, the presence of at least one SAE/SAE suspected to be related to study treatment/non SAE has to be checked in a block e.g., among AE's in a ≤ 1 day gap block, if at least one SAE is occurring, then one occurrence is calculated for that SAE.

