2.8.2 Deaths

Any deaths up to and including Week 24 will be included in a separate AE table by treatment group for Week 24 analysis summarizing fatal events. Additional deaths in Epoch 4 will be included in a separate AE table similarly for the End of study analysis.

Deaths will also be listed by treatment groups for both Week 24 analysis and End of study analysis.

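### As written, the overall 48-week adverse event summaries cover only subjects who enter Epoch 4, which conflicts with the all-subjects safety objective and with the SAP's own full-SAF tables

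*SAP*

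**What the plan says.** **Population rule.** SAP 2.8 uses the full SAF for the Week 24 safety analyses, but "all End of study safety analyses will be performed for subjects in the SAF who enter Epoch 4". Protocol 9.5.2.2 opens the same way: "All safety analyses will be performed for subjects in the SAF who enter Epoch 4". SAP 2.2 defines the Epoch 4 safety set as "all SAF subjects who received at least one dose of Epoch 4 study medication".

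**Overall summaries.** Protocol 9.5.2.2 lists Epoch 4 tables of AEs, SAEs, AEs leading to permanent discontinuation and other significant AEs, then adds: "Similar summaries will be provided for events occurred during the overall 48 weeks of Epoch 3 plus Epoch 4". SAP 2.8.1, under its End of study heading, says: "Overall treatment emergent AEs for the overall 48 weeks of Epoch 3 plus Epoch 4 by 10 randomized treatments will be generated". That SAP sentence names no analysis set.

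**Objective.** Protocol 2.2, objective 5, covers safety and "tolerability of LIK066 over 24 weeks of treatment and over 48 weeks of treatment for all subjects".

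**Other outputs.** SAP 2.8.1 plans registry tables by "10 randomized treatment arms on the SAF for overall study duration", and a listing of every AE in the database. On deaths after Week 24, SAP 2.8.2 says: "Additional deaths in Epoch 4 will be included in a separate AE table similarly for the End of study analysis".

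**The concern.** Entry to Epoch 4 is a post-randomization event that depends on how the subject tolerated Epoch 3. Protocol 5.6.2 requires treatment to stop for ketoacidosis or lower limb amputation, and protocol Appendix 2 requires it for a potential Hy's law case. A subject with such an event in Epoch 3 takes no Epoch 4 dose. A 48-week table restricted to entrants would leave out both the subject and the event, and would describe people already selected for having stayed on drug through the first period.

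There is also a gap after Week 24. Subjects who stop treatment are not withdrawn, and protocol 5.6.2 keeps collecting their AEs and SAEs. Under SAP 2.8.1, events after discontinuation still count as treatment-emergent. An event at Week 30 in someone who stopped at Week 10 is too late for the Week 24 analysis and lies outside the End of study population. At stake is whether the tables meant to answer objective 5 can answer it.

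**Working it through.** The documents give no figure for this point, so the check is mainly a comparison of populations, data cuts and outputs.

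**1. Does the entrant rule reach the 48-week summaries?** In the protocol, yes: the overall AE sentence stands in 9.5.2.2, directly under a rule covering all safety analyses there. Protocol 9.3 also limits overall exposure to SAF subjects who enter Epoch 4. In the SAP, the rule covers all End of study safety analyses, and the overall table sits under that heading in 2.8.1. The restriction is therefore the literal reading of the SAP, though the sentence itself is silent.

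**2. Does the restriction fit the SAP's other outputs?** No, in two places.
- The registry tables use the same 10 arms and the whole study, but the full SAF.
- SAP 2.4.1 reports overall exposure by 10 arms in categories that include ≤4 and >4–12 weeks. Overall duration is last dose minus first dose plus 1. A subject who reaches Epoch 4 after a 24-week Epoch 3 could hardly fall in either category, so those rows presuppose that subjects who stopped in Epoch 3 are included.

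**3. Where does each event go?** Taking entry to Epoch 4 to mean at least one Epoch 4 dose:

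| Event | Week 24 analysis (full SAF, cut at end of Epoch 3) | End of study and overall summaries (entrants) | Registry tables (full SAF) | AE listing |
|---|---|---|---|---|
| Epoch 3 AE leading to permanent stop | Yes | No | As an event, if serious or above 2% | Yes |
| Week 24–48 SAE in an Epoch 3 stopper | No | No | Yes | Yes |
| Week 24–48 non-serious AE above 2% in a stopper | No | No | Yes | Yes |
| Week 24–48 non-serious AE at or below 2% in a stopper | No | No | No | Yes |
| Week 24–48 AE of special interest in a stopper | No | No | Only by system organ class and preferred term, not by risk category | Yes |
| Week 24–48 death in a stopper | No | Not in the Epoch 4 death table | Yes, in the count of deaths from SAEs | Yes |

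The first row follows from the definition of the set: such events contribute zero to an entrant-only 48-week table at any rate of stopping.

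**4. Scale, for illustration only.** The randomization weights in protocol 9.8 (1:1:1:1:1:2:1:1:1:2) sum to 12. 432/12 = 36 subjects per unit weight, and 72 for weight 2. With an assumed share *d* not entering Epoch 4, the number omitted is N × *d*:

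| *d* (assumed) | Of 432 | Of a 72-subject arm | Of a 36-subject arm |
|---|---|---|---|
| 5% | 21.6 | 3.6 | 1.8 |
| 10% | 43.2 | 7.2 | 3.6 |
| 15% | 64.8 | 10.8 | 5.4 |
| 20% | 86.4 | 14.4 | 7.2 |

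For a 72-subject arm with *d* = 15% and half of the stops due to an AE (also assumed), 10.8 × 0.5 = 5.4 subjects, or 5.4/72 = 7.5%, have an Epoch 3 AE discontinuation. The entrant-only table shows 0 of 72 − 10.8 = 61.2 for these.

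**The case against.** The strongest reply is that the SAP does not mean to restrict the overall tables. SAP 2.1.1 separates an overall analysis (randomization baseline, 10 arms) from an End of study analysis using Epoch 4 data only. The overall AE sentence names no set, and the exposure categories point to a wider one. This stands as a reading of intent. It does not remove the defect, because SAP 2.8 covers all End of study safety analyses without exception and the protocol text is not ambiguous.

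Three stronger readings are tempting, and the documents do not support them.

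- *That these events are lost from reporting.* They are not. The registry tables cover SAEs, non-serious events above 2% and deaths from SAEs on the full SAF for the whole study, and the listing holds every AE. A Week 30 death in a Week 10 stopper misses the Epoch 4 death table but is still tabulated.
- *That dose-related intolerance is hidden.* The eight randomized dose regimens are given only in Epoch 3; every active subject takes 25 or 35 mg qd in Epoch 4. Intolerance at the Epoch 3 doses is assessed in the Week 24 analysis on the full SAF, including AEs leading to discontinuation and the dedicated diarrhea analyses. SAP 1.1 makes that the main analysis. Diarrhea, described in protocol 1.1 as very common, would also be expected to pass the registry threshold.
- *That about 65 subjects will be left out because the plan assumes 15% loss.* The 15% is a power allowance (432 × 0.85 = 367.2, the stated 367), not a forecast of who will fail to enter Epoch 4.

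Limiting summaries that begin at the switch to subjects who made the switch is ordinary practice and is not at issue.

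**Conclusion.** The concern holds for the overall 48-week AE summaries and for the handling of events after Week 24 in subjects who stopped in Epoch 3. As written, the 48-week summary excludes every AE that led to permanent discontinuation in Epoch 3, contrary to objective 5 and out of line with the SAP's registry tables and exposure categories. Two 48-week tables by the same arms could carry different denominators in one report. For subjects who stopped in Epoch 3, AEs of special interest after Week 24 have no dedicated summary, and non-serious events at or below 2% are certain to appear only in the listing.

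The conclusion rests on the literal population rule and on reading entry to Epoch 4 as at least one Epoch 4 dose. It needs no assumed rate. Only the number of subjects affected does, and the documents do not give it.

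**What to change.** - In SAP 2.8 and 2.8.1 and protocol 9.5.2.2, state that the overall (Epoch 3 plus Epoch 4) summaries of AEs, SAEs, AEs leading to discontinuation and AEs of special interest use the full SAF by the 10 randomized arms, including events after Week 24 in subjects who did not enter Epoch 4.
- Keep the Epoch 4 safety set for summaries that start at the Epoch 4 switch.
- In SAP 2.8.2, count all deaths after Week 24 in SAF subjects, whether or not they entered Epoch 4.

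The cost is revised wording, a different population flag and minor reprogramming; no new data are needed. The likely price is slightly less favourable 48-week incidences, because subjects who stopped early return to both numerator and denominator.
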